### **Physical Examination**

A physical examination including evaluation of extra intestinal manifestations will be performed at the designated study visits as specified in [Table 1](#).

A full physical examination will be performed at Screening, Baseline, Week 16 and Week 52/ET Visit and must include an assessment of extra-intestinal manifestations (EIMs) and a count of the number of cutaneous fistulas. Symptom-based physical examinations will be performed at all other visits must include a count of the number of cutaneous fistulas.

The physical examination at the Baseline Visit will serve as the Baseline physical examination for the entire study. A count of the number of cutaneous fistulas draining upon gentle compression must be performed during each physical exam. Fistulas will be classified as abdominal or perianal/anal. Physical examination abnormalities noted by the

Investigator at Baseline prior to the first dose of study drug (including fistulas and fissures) will be recorded in the subject's medical history. Abnormalities noted after the Baseline Visit and first dose of study drug will be evaluated and documented by the Investigator as to whether or not these are adverse events. All findings whether related to an adverse event or part of each subject's medical history will be captured on the appropriate eCRF page.

A symptom-directed physical examination will be performed when necessary.

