**CDAI**

A CDAI will be calculated from a subject diary, physical exam, and appropriate laboratory values at all study visits beginning at Screening. The Screening Period will be a minimum of 7 days but will not exceed 35 days. The CDAI calculated during Screening will serve as the Baseline CDAI.

For calculation of CDAI scores, beginning with the Week 2 through Week 52, the CDAI scores must be calculated using a hematocrit value from the preceding visit laboratory work.

CDAI at Visit	Hematocrit Value Utilized
Week 2	Baseline
Week 4	Week 2
Week 8	Week 4
Week 12	Week 8
Week 16	Week 12
Week 20	Week 16
Week 28	Week 20
Week 36	Week 28
Week 44	Week 36
Week 52	Week 44

For calculating CDAI, to answer questions one (1) through three (3), entries from the 7 days prior to the day of study visit should be used as recorded by the subject from the diary.

Diary entries should not be included in the 7 days evaluated prior to the visit if: (1) the day the subject received medication for bowel preparation prior to endoscopy, (2) the day the subject underwent an endoscopy, and (3) 2 days following the endoscopy. Earlier diary entries will be used accordingly in order to provide the most recent data for 7 days prior to the respective study visit.

For the CDAI questions regarding presence of anal fistulas and other fistulas, all fistulas detectable on physical examination (draining and non-draining) should be captured on the CDAI and calculated into the CDAI score.

When completing question five (5) ("Taking Lomotil/Imodium/Loperamide/opiates for diarrhea, 0 = no, 1 = yes") on the CDAI, "no" should be answered if a subject is taking an opiate(s) solely for pain.

For question seven (7), hematocrit results from central laboratory will be used for the CDAI calculation. If the hematocrit value contains more than one decimal point, the rounding will be allowed to the tenths decimal (e.g., Hematocrit value 33.44 will be captured as 33.4, Hematocrit value of 33.45 will be captured as 33.5). The Hematocrit values either prior to completing the calculation or at the subtotal box 7 of the CDAI should not be rounded to a whole number.

The height obtained at Screening should be used when selecting the standard weight in [Appendix E](#), and this standard weight should be used for calculating every CDAI throughout subject participation in the study.

Standard height is calculated by using the height obtained at Screening (without shoes) plus one inch.

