Subjects in whom the CD-related corticosteroids (systemic or rectal corticosteroids) that were not being taken at Baseline and are initiated during the study or who have equivalent dose of these medications increased to greater than the dose taken at Baseline will be censored for efficacy assessments (i.e., will be considered non-responders for categorical endpoints and will have Baseline values carried forward for non-categorical assessments) from that point through the end of the study. These subjects will continue to be evaluated in the safety population.

The equivalent steroid dose will be determined based on the table below:

| Corticosteroid | Equivalent Dose (mg) |
|--------------------|----------------------|
| Cortisone | 25 |
| Hydrocortisone | 20 |
| Prednisone | 5 |
| Prednisolone | 5 |
| Triamcinolone | 4.0 |
| Methylprednisolone | 4.0 |
| Betamethasone | 0.75 |
| Dexamethasone | 0.75 |
| Budesonide | 1 |
| Beclomethasone | 5 |
| Beclometasone | 5 |

Definition of Missing Data Imputation

The following imputation methods will be used to impute missing values in the efficacy analyses. In addition, an observed case analysis will be performed.

Non-Responder Imputation (NRI)

The NRI approach is used for binary efficacy variables. These variables can take values of 'Achieved' or 'Not Achieved' or may be missing for any reason including discontinuation from study. According to the NRI imputation approach, all missing values will be considered as 'Not Achieved.'

Last Observation Carried Forward (LOCF)

For all variables (categorical variables and continuous variables), the following rules will be used for the LOCF approach:

1. Baseline and Pre-Baseline values will not be used to impute the missing Post-Baseline values.

2. Missing values after Study Day 1 will be imputed using the latest non-missing values after Day 1 and prior to the missing value. If there are no non-missing values after Baseline, then the LOCF value will be missing.

Observed Case (OC)

Observed case analysis will be performed such that missing values will not be imputed.

However, all observed values will be replaced by Baseline value once subjects received CD-related corticosteroid therapy.

Mixed-Effect Model Repeated Measure (MMRM)

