- The proportion of subjects who achieve $> 50\%$ reduction from Baseline in SES-CD or endoscopic remission at Week 12/16.
- The proportion of subjects who achieve modified clinical remission at Week 16 among subjects with an average daily SF ≥ 4.0 or average daily AP ≥ 2.0 at Baseline.

For categorical efficacy endpoints for Induction Period, the pairwise comparisons for the difference in proportions of subjects between treatment groups and placebo group will be analyzed using the CMH test adjusted for Crohn's disease severity (SES-CD < 15 , ≥ 15) at Baseline. Additionally, the CMH-based 95% confidence interval for the difference in proportions will be provided. The 95% confidence interval for the difference in proportions within each Crohn's disease severity (SES-CD < 15 , ≥ 15) at Baseline category will be calculated based on normal approximation.

The non-responder imputation will be used for subjects with missing data at the endpoint evaluated. The last observation carried forward (LOCF) method will also be used as the sensitivity analyses for the secondary endpoints.

In general, continuous secondary efficacy variables with repeated measurements will be analyzed using a Mixed Effect Repeated Measure (MMRM) model. The mixed model includes the categorical fixed effects of treatment, Crohn's disease severity (SES-CD < 15, ≥ 15) at Baseline, week and treatment-by-week interaction and the continuous fixed covariates of baseline measurement. An unstructured variance-covariance matrix will be used. If convergence is not achieved, other variance-covariance matrix will be explored until coverage. The parameter estimations will be based on assumption of data being missing at random and using the method of restrictive maximum likelihood (REML).

Continuous secondary efficacy variables will also be analyzed using an Analysis of Covariance (ANCOVA) model including factors for treatment group and Crohn's disease severity (SES-CD < 15, ≥ 15) at Baseline, and Baseline values as a covariate. The MMRM analysis is considered primary for inferential purposes.

The additional endpoints include:

- Proportion of subjects who achieve clinical remission over time in Induction Period.
- Proportion of subjects who achieve clinical response over time in Induction Period.
- Proportion of subjects who achieve CDAI < 150 over time in Induction Period.
- Proportion of subjects with decrease in CDAI ≥ 70 points from Induction Baseline over time in Induction Period.

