- Proportion of subjects with decrease in CDAI ≥ 100 points from Induction Baseline over time in Induction Period.
- Proportion of subjects who are IBDQ responders (increase in IBDQ score ≥ 16 points from Induction Baseline) over time in Induction Period.
- Proportion of subjects with IBDQ score ≥ 170 over time in Induction Period.
- Proportion of subjects who achieve steroid-free CDAI < 150 over time in Induction Period among subjects taking corticosteroids at Baseline.
- Proportion of subjects who achieve steroid-free clinical remission over time in Induction Period among subjects taking corticosteroids at Baseline.

- Change from Induction Baseline in fecal calprotectin level over time in Induction Period.
- Change from Induction Baseline in hs-CRP over time in Induction Period.
- SES-CD endpoints without any missing individual variables.
- The proportion of subjects with no anal fissures at Week 16 among subjects with anal fissures at Baseline.
- The proportion of subjects with no draining fistulas at Week 16 among subjects with draining fistula at Baseline.
- The proportion of subjects with no non-draining fistulas at Week 16 among subjects with non-draining fistula at Baseline.
- The proportion of subjects with no any fistulas at Week 16 among subjects with any fistula at Baseline.
- Change from Induction Baseline in Bristol Stool Chart at Week 4 and Week 16.
- The proportion of subjects who achieve Bristol Stool Chart response at Week 4 and Week 16.
- Cross tabulation of Baseline and Week 16 in EIM.
- The proportion of subjects who achieve modified clinical remission at over time in Induction Period among subjects with an average daily SF ≥ 4.0 or average daily AP ≥ 2.0 at Baseline.
- Change from Induction Baseline in EQ-5D over time in Induction Period.
- Change from Induction Baseline in WPAI over time in Induction Period.

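### The Induction SAP's non-draining fistula endpoint scores a subject as a success when the fistula has begun to drain and no non-draining fistula remains

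*SAP*

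**What the plan says.** The Induction SAP, Section 10.3, has three neighbouring fistula rows among the additional endpoints:

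- Draining row: "The proportion of subjects with no draining fistulas at Week 16 among subjects with draining fistula at Baseline".
- Non-draining row: "The proportion of subjects with no non-draining fistulas at Week 16 among subjects with non-draining fistula at Baseline".
- Any-fistula row: "The proportion of subjects with no any fistulas at Week 16 among subjects with any fistula at Baseline".

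The protocol's own fistula endpoints (Section 5.3.3.3) concern draining fistulas only. The non-draining row appears first in the Induction SAP, and the text available gives no rationale for its wording. The Extension SAP's endpoint list (Section 10.2) has no fistula row.

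Draining status is reassessed through the study. Protocol Section 5.3.1.1 (Physical Examination) states: "A count of the number of cutaneous fistulas draining upon gentle compression must be performed during each physical exam". The CDAI text in the same section recognises both kinds: "all fistulas detectable on physical examination (draining and non-draining) should be captured on the CDAI and calculated into the CDAI score".

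Two general rules might have acted as a guard. For missing data, Section 10.3 says: "The non-responder imputation will be used for subjects with missing data at the endpoint evaluated". For subjects who start CD-related corticosteroids or go above their Baseline dose, Section 6.0 says they "will be considered non-responders for categorical endpoints".

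**The concern.** The draining and non-draining rows look symmetrical but are not. Leaving the draining class, by closing or by ceasing to drain, is an improvement either way. Leaving the non-draining class can be an improvement (closure) or a deterioration (onset of drainage). The non-draining row counts both exits as success.

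At stake is the reading of one between-arm comparison. Section 10.3 prescribes a CMH comparison with placebo and a 95% confidence interval for categorical efficacy endpoints in induction, and protocol Section 8.1.6.3.1 has additional endpoints analysed in the same way as secondary ones. If conversion to drainage differs between arms, the difference in this row mixes a benefit with a harm.

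**Working it through.** The plan attaches no figure to this endpoint, so there is none to reproduce. The check applies the three rows, as worded, to each possible change from Baseline to Week 16.

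**Step 1. One fistula, non-draining at Baseline.**

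| Week 16 status | Draining row | Non-draining row | Any-fistula row |
|---|---|---|---|
| Closed | not in denominator | success | success |
| Still non-draining | not in denominator | failure | failure |
| Draining | not in denominator | **success** | failure |

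The last line is the fault. The draining row cannot catch it, because its denominator requires a draining fistula at Baseline.

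**Step 2. Two fistulas, both non-draining at Baseline.** Scoring is by subject. One closed and one draining, or both draining, is a success on the non-draining row and a failure on the any-fistula row. If either fistula is still non-draining, the subject fails both. So conversion produces a false success only when no non-draining fistula is left.

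**Step 3. One draining and one non-draining at Baseline.** Selected outcomes:

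| Draining one becomes | Non-draining one becomes | Draining row | Non-draining row | Any-fistula row |
|---|---|---|---|---|
| Closed | Draining | failure | **success** | failure |
| Draining | Draining | failure | **success** | failure |
| Non-draining | Closed | success | **failure** | failure |
| Non-draining | Non-draining | success | failure | failure |
| Draining | Closed | failure | success | failure |

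The first two lines repeat the fault, though here the draining row records the failure. The third is the reverse error: both fistulas improved, yet the subject fails. In the fourth, the Baseline non-draining fistula is still there, so failure is the right answer to the question this row asks.

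**Step 4. Possible guards.** Non-responder imputation acts on missing data, and a fistula seen to drain is observed data. The corticosteroid rule is triggered by steroid use, not by drainage. Neither changes the scores above.

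**Step 5. Size.** With one fistula per subject, closure rate c and conversion-to-draining rate q:

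- rate as written = c + q
- rate with a guard against draining fistulas = c
- overstatement = (c + q) − c = q

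Neither c nor q is in the documents. As an assumed range only, c from 0.10 to 0.30 and q from 0 to 0.30 give an as-written rate from 0.10 + 0 = 0.10 to 0.30 + 0.30 = 0.60, against 0.10 to 0.30 with the guard.

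**Step 6. Contrast with placebo.** For arms A and P, difference as written = (c_A − c_P) + (q_A − q_P). Equal conversion rates cancel. For the sign to reverse, the conversion difference must oppose the closure difference and exceed it. Assumed example: c_A = 0.30, q_A = 0, c_P = 0.20, q_P = 0.20. The closure difference is 0.30 − 0.20 = +0.10; the row gives 0.30 − 0.40 = −0.10. Nothing in the documents shows whether rates like these occur.

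**The case against.** The strongest reply is that the any-fistula row sits in the same list, includes every subject in question, and scores each converted fistula as a failure. A rise in the non-draining row without a rise in the any-fistula row would be visible to a careful reader. The row is also only an additional endpoint: it is not co-primary, not in the secondary list, not used in the MCPMod dose selection, and not carried into the extension. All of this stands and keeps the point minor. It does not make the row right, since the same subject is a success in one table and a failure in another.

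A reader might go on to infer more than the documents support:

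- *That the endpoint generally penalises improvement.* It does so in the third line of Step 3, where the draining fistula persists without draining and the non-draining one closes. If the Baseline non-draining fistula is still present, failure is correct.
- *That the comparison with placebo points the wrong way, or is inflated by a known amount.* That needs a difference in conversion between arms, and the documents give neither rates nor the number of subjects with fistulas. No entry criterion requires a fistula.
- *That the SAP calls this outcome healing.* The row does not use that word.
- *That separate non-draining counts are already recorded.* The CDAI form (protocol Appendix D) pools draining and non-draining fistulas within checklist items. A non-draining count has to be derived.

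**Conclusion.** The row is wrong as worded for an identifiable class of subjects: those whose non-draining fistulas have begun to drain and who have no non-draining fistula left at Week 16. This follows from the text alone, given that drainage can change between examinations. With one fistula per subject the overstatement equals the conversion rate; its actual size is unknown, and the ranges in the working are assumptions. The reverse error is real but confined to the pattern described. The any-fistula row is correctly directed for converted fistulas and limits the damage. The co-primary and dose-selection conclusions are unaffected. Severity: minor.

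**What to change.** Either of two changes will do.

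1. Add to the success condition that no draining fistula is present at Week 16. This makes every converted fistula a failure. The row then becomes the any-fistula row restricted to subjects with a non-draining fistula at Baseline. It does not remove the reverse error, and it also fails a mixed-Baseline subject whose non-draining fistula closed while the other went on draining (last line of Step 3).
2. Replace the row with a cross-tabulation of fistula status (none, non-draining, draining) at Baseline by Week 16, classifying each subject by the worst status present. This shows closure, conversion and cessation of drainage separately, and so deals with both errors. The same SAP list already plans a cross-tabulation of this kind for extra-intestinal manifestations.

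The cost is one line of wording or one table. Non-draining counts can be derived as total minus draining cutaneous fistulas, since the protocol (Table 1 footnotes and Physical Examination) asks for both at each examination. This assumes the two counts are stored separately, which should be confirmed against the case report form. The Extension SAP (Section 3.0) says the Induction SAP was signed off before the December 2016 induction lock, so the change would be a documented clarification or a supplementary table in the report.

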10.4 Handling of Multiplicity

The MCP step in MCPMod approach will typically be performed using an efficient test for trend, adjusting for the fact that multiple candidate dose response models are being considered.

10.5 Efficacy Subgroup Analysis

The subgroups listed below will be used in subgroup analyses of the co-primary endpoints.

- Sex (male, female)
- Age (\leq median, $>$ median)
- Race (white, non-white)
- Baseline fecal calprotectin (\leq median, $>$ median)
- Baseline fecal calprotectin ($\leq 250 \mu\text{g/g}$, $> 250 \mu\text{g/g}$)
- Baseline corticosteroid use (yes, no)
- Baseline immunosuppressant use (yes, no)
- hs-CRP at Baseline (< 10 and $\geq 10 \text{ mg/L}$)
- hs-CRP at Baseline (\leq median, $>$ median)
- Crohn's disease severity (CDAI ≤ 300 , > 300) at Baseline
- Baseline CDAI (\leq median, $>$ median)
- Baseline SES-CD (\leq median, $>$ median)
- Baseline SES-CD (< 15 , ≥ 15)
- Weight (\leq median, $>$ median)
- Baseline albumin (\leq median, $>$ median)
- Disease duration (≤ 3 years, > 3 years)
- Disease duration (\leq median, $>$ median)
- Region (US, ex-US)
- Prior anti-TNF status (prior anti-TNF, prior anti-TNF naïve)

11.0 Safety Analysis

11.1 General Considerations

Adverse events (AEs), laboratory data and vital signs are the primary safety parameters in this study. All safety comparisons will be performed between treatment groups using the

safety analysis set. The safety variable will be summarized by treatment according to the treatment a subject actually received. The differences between treatment groups and placebo in safety parameters will be evaluated using two--sided tests at the significance level of 0.100.

11.2 Analysis of Adverse Events

11.2.1 Treatment-Emergent Adverse Events

Treatment-emergent AEs for double-blind Induction period are defined as events that begin or worsen either on or after the first dose of the study medication and within 30 days after the last dose of the study medication for who subjects who discontinued study prior to double-blind Extension Period or up to the first dose of double-blind Extension Period for subjects who received at least a dose of study medication during double-blind extension period. An overview of treatment-emergent AEs, including AEs of special interest such as adverse events leading to death and adverse events leading to early termination, AEs by Medical Dictionary for Drug Regulatory Activities (MedDRA version 18.1 or later) preferred term and system organ class, AEs by maximum relationship to study drug, and AEs by maximum severity will be summarized by number and percentage. Treatment group differences (each ABT-494 dose group versus placebo group, as well as ABT-494 dose groups combined versus placebo group) in the overall incidence of treatment-emergent AEs will be assessed with Fisher's exact test for each preferred term for double-blind induction period.

Changes in laboratory data will be described using statistical characteristics and compared between treatment groups and placebo will be performed using a one-way Analysis of Variance (ANOVA). In addition, shift tables and listings will be provided for abnormal values, whereby the normal range of the analyzing laboratory will be used. Vital signs will be analyzed similarly.

The number and percent of subjects experiencing treatment-emergent adverse events will be summarized for the following adverse event categories. Comparisons of the percent of subjects experiencing an adverse event between treatment groups and placebo will be

performed using Fisher's exact tests. Only P values < 0.100 when rounded to three digits will be presented.

- Any treatment-emergent adverse event.
- Any treatment-emergent adverse event that was rated as possibly related to study drug by the investigator (Reasonable Possibility).
- Any treatment-emergent severe adverse event.
- Any treatment-emergent serious adverse event.
- Any treatment-emergent adverse event leading to discontinuation of study drug.
- Any treatment-emergent adverse event leading to death.
- Any treatment-emergent adverse event of special interest.

Treatment-emergent adverse events will be summarized as follows:

- Grouped by System Organ Class and Preferred Term.
- A by-subject listing will be provided.
- Grouped by System Organ Class, Preferred Term and Severity.
- Grouped by System Organ Class, Preferred Term and Relationship to Study Drug.
- Grouped by System Organ Class and Preferred Term with subject numbers.

In treatment-emergent AE tables, a subject who reports more than one treatment-emergent AE in different system organ classes will be counted only once in the overall total. A subject who reports two or more different preferred terms which are in the same SOC will be counted only once in the SOC total. A subject who reports more than one treatment AE with the same preferred term will be counted only once for that preferred term using the most extreme incident (i.e., most "severe" for the severity tables and most "related" for the relationship tables).

Adverse events will also be summarized by maximum severity. If a subject has an adverse event with unknown severity, then the subject will be counted in the severity

category of "unknown," even if the subject has another occurrence of the same adverse event with a severity present. The only exception is if the subject has another occurrence of the same adverse event with the most extreme severity – "Severe." In this case, the subject will be counted under the "Severe" category.

Adverse events will also be summarized by maximum relationship to study, as assessed by the investigator. If a subject has an adverse event with unknown relationship, then the subject will be counted in the relationship category of "unknown," even if the subject has another occurrence of the same adverse event with a relationship present. The only exception is if the subject has another occurrence of the same adverse event with a relationship assessment of "Reasonable Possibility." In this case, the subject will be counted under the "Reasonable Possibility" category, respectively.

Incidence rates per 100 patient years of exposure to study drug will be presented for AE overviews and for AEs by SOC and preferred term where the number of events will be used as the numerator.

